9.3 Definition of Populations

Study population includes older adults (age 60 y.o. and older) with the current diagnosis of major depression without dementia who have been on stable treatment for at least 4 months, but still have moderate – severe depressive symptoms. ITT analyses will be on all the subjects who were randomized and who had baseline assessments. Per protocol population will be the subset of the ITT subjects who attended at least 80% of the sessions and who had no major protocol violations such as hospitalization, adverse events and stopping of medication.

9.4 Interim Analyses and Stopping Rules

We will not conduct interim analyses on primary outcomes.

- If a patient demonstrates worsening of their depressive symptoms by week 12 (i.e., CGI-I score > 4) of treatment, they will be discontinued from the study and referred for appropriate clinical services.
- Suicidal ideations with the HAMD item 3 score of 3 or greater
- Other SAEs.
- Engagement in alternative treatments interfering with the primary outcomes of the interventions

All dropouts will be analyzed by the reason for termination and the reasons will be classified as:

- a) Lack of efficacy; b) Side-effects; c) Lost-to-follow up; d) Hospitalization; e) Death; f) Other
- Relation to the study interventions: a) likely; b) probable; c) unlikely.

9.5 Outcomes

Measures and Outcomes: All instruments provide a comprehensive assessment of the severity of depression, health related quality of life, medical comorbidity, cognitive and functional

impairment, life satisfaction and quality of life and will enable the PI to compare results of the study to other investigations. Diagnosis will be determined on study entry. *All outcome measures will be administered at baseline, week 12, 6 months, and 12 months or upon early termination. Mood, anxiety, and safety measures will be administered at all visits.*

9.5.1 Primary Outcome

Primary outcomes include measures of depressive symptom severity. Primary outcomes will be measured and defined as follows: 1) continuous outcome of change in HAMD scores;

9.5.2 Secondary Outcomes

Secondary outcomes include remission status, global improvement, cognition and memory domains, and fMRI neural correlates of working memory, and brain structure. Worsening of depressive symptoms and relapse to major depressive episode will be determined during 6 and 12 month follow-up visits. We will investigate whether variations in emotional regulation will moderate or predict emotional and functional improvement linked with TCC compared to the control condition

Exploratory outcomes and biomarkers – multimodal MRI analyses, changes in gene expression and peripheral pro-inflammatory cytokines associated with clinical response to the interventions.

9.6 Data Analyses

Statistical Analysis Plan.

The study will include 220 subjects assigned to TCC/HEW in a 1:1 ratio, within each treatment arm. Prior to performing the primary analyses, descriptive statistics and graphical summaries will be obtained for the primary outcomes (HAMD-24 (Aim 1), connectivity in DMN in rs-fMRI and BOLD activation during the mood task in the anterior cingulate (Aim 2)) to check for outliers and violations of model assumptions and to assess the need for transformations or non-parametric methods. We will also plot each of the primary measures as a function of time to examine the form of the longitudinal trajectories. (HAMD-24 scores will be recorded every 2 weeks throughout the intervention.) Longitudinal analysis proposed will rely on generalized linear mixed models (GLMMs). GLMMs properly account for correlations induced by repeated measurements within subjects, allow for both fixed and time-varying covariates and automatically handle missing data, producing unbiased estimates as long as observations are missing at random. This allows the use of all available data from all subjects, thereby minimizing the effects of loss to follow-up. To make the most efficient use of our data we will fit a single model using all time points for each outcome. Our specific aims and hypotheses correspond to specific contrasts within those models. Demographic variables (e.g., age, gender, etc.) and variables characterizing the course of depressive symptoms (e.g., age of onset, chronicity, number of episodes, length of the current episode, etc.) will be compared by treatment group and examined in relation to outcome variables; this would define one possible set of appropriate covariates, if needed.

Aim 1: Primary analysis: Our primary analysis will consist of a GLMM for HAMD-24 with treatment group effects and time main effects, along with two-way interactions of time and group. The primary analysis will assess treatment effects at the end of treatment at 12 weeks. Our primary analysis is valid under the assumption of missing-at-random. To study missingness patterns, we will compare mean response trajectories of the primary outcome measure HAMD for subjects who dropped out and those who did not. We will further compare treatment groups for drop-out rates, time to drop-out and drop-out reasons. Since it is theoretically impossible to rule out data missing-not-at-random, we will also perform sensitivity analysis taking a pattern mixture approach. Our pattern mixture approach will make assumptions on how the outcome trajectory

for subjects who dropped out will differ from those for subjects who did not. These differences will be allowed to be vary across treatment arms and the amount of difference will be varied in a plausible range to obtain a full sensitivity analysis.

Secondary analysis: Treatment maintenance will be assessed via the GLMM at follow-up as part of the secondary analysis. Secondary analysis will also include comparison of remission status (binary outcome) at the end of treatment between treatment groups via a logistic regression. Analyses for secondary outcomes clinical global improvement (CGI) and cognitive domain scores in the executive function and memory domains will be similar to those above for the continuous HAMD scores. As noted in the Neuropsychological Assessment section, there are 4 cognitive domains that are being assessed. Of these, the two primary cognitive domains of interest for this proposal are executive function and memory. A separate GLMM as above will be estimated using these 2 domain scores as dependent variables. In addition treatment adherence and time in practice will be considered as moderators of treatment effects in the longitudinal modeling of primary depression and imaging outcomes in the first two aims.

Aim 2. Hypothesis 2a, b: Primary analysis: Similar to Aim 1, the primary outcomes of DMN connectivity in rs-fMRI and BOLD activation during the mood task in the anterior cingulate will be modeled with a GLMM model with treatment group and time as main effects, along with their two-way interaction. Significant interactions would suggest differential trajectories over time for activation and connectivity outcomes in the two treatment groups. Primary analysis will assess treatment effects at 12 weeks in the primary outcomes. Sensitivity to missing data will be studied as explained in detail in Aim 1. The outcomes of DMN connectivity in rs-fMRI and BOLD activation will be treated as co-primary endpoints and further we will carefully examine the effect size of each co-primary endpoint to ensure clinically meaningful treatment effect.

Secondary analysis: Secondary measures for Aim 2 will be BOLD activation during the cognitive task in hippocampus. Secondary analysis will include assessment of treatment maintenance effects on the primary and secondary outcomes and of treatment effects during treatment in the secondary outcome of BOLD activation during the cognitive task in hippocampus.

Exploratory Hypothesis 2c: Exploratory analysis: Exploratory variables will include hippocampal and anterior cingulate volume and white matter high intensity. To test hypotheses about the relationships between the imaging metrics and the primary outcomes in mood and cognition, we will derive domain summary scores for the 2 cognitive domains of interest, memory, and executive function. We will assess treatment moderator effects of baseline hippocampal and anterior cingulate volume and white matter high intensity on HAMD and memory and executive function domain scores. Statistical evaluation of moderators will be done by including the posited moderator variable as an independent variable and evaluating the moderator x treatment group interaction term in the GLMM models proposed in Aim 1. In addition we will assess the treatment mediator effects of change in DMN connectivity on change in HAMD and memory and executive function domain scores. Mediation effects will be assessed via multiple regression models, where the posited mediator variable is regressed on treatment, outcome is regressed on treatment and the outcome is regressed on the mediator and the treatment. For confirmation of the mediation effect, treatment effects need to be found significant on the outcome and the mediator as well as a decreased treatment effect size on the outcome in the presence of the mediator.

Exploratory aim 1: We will explore the difference in changes in gene expression and peripheral pro-inflammatory cytokines associated with clinical response to the interventions, by comparing the change in these markers between the two intervention groups and by examining how the change in these markers correlate with changes in depression and cognitive scores in the two groups.

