9.2 Sample Size and Randomization

Power and sample size estimate: We assume that dropout will be at 10% and 20% at the end of 12 week treatment phase and 6 and 12 month follow-up, respectively. For Aim 1, if the treatment main effects are linear over the 12 week treatment phase on HAMD, our design with 7 time points (baseline, 2, 4, 6, 8, 10, 12 weeks) and with complete data on 99 subjects within each arm (10% dropout) will have 80% power at significance level $\alpha=0.05$ for detecting a treatment and time interaction corresponding to no difference at baseline and a difference of $d = 0.32$ SDs between any two arm at the end follow-up. Our R21 project found an effect size of 0.65 in HAMD between TCC and HEW at 12 weeks. If treatment effects continue to grow linearly over the 6 and

12 month follow-up, our design with complete data on 88 subjects within each arm (20% dropout) will have 80% power at significance level $\alpha=0.05$ for detecting a group difference between any two arms of $d = 0.36$ SDs at 6 and 12 month follow-up. The reported power is based on number of subjects with complete data, and hence is a conservative estimate of the actual power of our design, since the proposed GLMM framework utilizes all observed data collected from all subjects. In addition, the reported power analysis is based on a correlation of 0.5 between measurements obtained at different time points. Selection of the covariance structures within the GLMM model will be based on likelihood ratio test and/or AIC (Akaike Information Criterion). If we find either significant interactions or main effects, follow-up contrasts will be used to determine at which time points there has been significant change and/or differences in treatment effects relative to baseline.

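### Covariates for the primary models may be chosen from the trial's own arm differences and outcome associations, and the plan does not say whether the adjusted or unadjusted model is primary, so 5% control is not guaranteed

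*Combined protocol and SAP*

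**What the plan says.** Section 9.6 (Data Analyses), before the aim-specific models, names age and gender as example demographic variables. As illness-course variables it names age of onset, chronicity, number of episodes and length of the current episode. Both lists are open-ended. These variables "will be compared by treatment group and examined in relation to outcome variables; this would define one possible set of appropriate covariates, if needed". No threshold, final list or decision step is given.

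For Aim 1 the same section defines the primary model as "a GLMM for HAMD-24 with treatment group effects and time main effects, along with two-way interactions of time and group", and adds: "The primary analysis will assess treatment effects at the end of treatment at 12 weeks". Aim 2 uses the same form for its two co-primary imaging outcomes. Neither paragraph says that the covariate-free model remains primary whatever the covariate step produces.

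Three other parts bear on this:
- The opening of section 9 keeps adherence and time in practice out of the primary model. It is silent on baseline covariates.
- Section 6.2.2 stratifies randomisation by site and imaging (yes or no). Neither factor is named in the model.
- Section 6.2.3 adds control for instructor if several teach, and blinds both statisticians, with the groups coded 1 and 2.

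**The concern.** The sentence does more than leave out a list. It describes a way for covariates to emerge from two data-dependent sources: observed differences between arms, which under randomisation are chance, and associations with the trial's own outcomes. It calls the result one candidate set among others and makes its use optional. An analyst could report an unadjusted result, an adjusted one, or one adjusted for another set, and each would comply with the plan.

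Two things are at stake. If the choice is made with the results in view, the false-positive rate for the primary comparison exceeds 5%. If covariates enter only when they look imbalanced, the strong prognostic ones are usually left out, and the precision that planned adjustment would have bought is lost.

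**Working it through.** **1. Reproduce the plan's own figure.** Inputs from section 9.2: 99 per arm, visits at weeks 0, 2, 4, 6, 8, 10 and 12, correlation 0.5, alpha 0.05, power 80%. The tested effect is described as "for detecting a treatment and time interaction corresponding to no difference at baseline".

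- Sxx = 36 + 16 + 4 + 0 + 4 + 16 + 36 = 112
- SE of the week-12 difference = 12 × √(2(1 − 0.5)/(99 × 112)) = 0.114
- Detectable d = (1.960 + 0.842) × 0.114 = 0.319

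This matches the stated 0.32 (two-sided; one-sided gives 0.283). The power statement thus rests on a linear group-by-time contrast.

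**2. Does covariate choice move that contrast?** A baseline covariate entered as a main effect adds the same amount at every visit, so it cancels from week 12 minus baseline. Check: 200 simulated seven-visit data sets, fitted with and without six covariates (joint R² 0.30 with HAMD, an assumption), variance components held at their true values.

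| Contrast | Dropout | Median change in Z | Maximum |
|---|---|---|---|
| Group-by-time (week 12 minus baseline) | 0% | 0 | about 10⁻¹⁴ |
| Group-by-time | 10% | 0.04 | 0.24 |
| Week-12 group difference | 0% | 0.42 | 1.87 |
| Week-12 group difference | 10% | 0.36 | 1.61 |

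The choice matters for a week-12 group difference and hardly at all for the group-by-time contrast with main-effect covariates. Covariate-by-time terms would not cancel.

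**3. Error rate for a week-12 group difference.** Null simulation, 99 per arm, 4,000 runs per column (Monte Carlo SE about 0.35 points). Six independent covariates are assumed, one for each variable named in section 9.6. The documents give no prognostic strength, so joint R² is varied. All thresholds are assumptions too.

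| Procedure | R² 0 | R² 0.12 | R² 0.30 |
|---|---|---|---|
| Unadjusted, fixed | 4.9% | 4.9% | 5.5% |
| All six, fixed | 5.2% | 5.3% | 5.2% |
| Select if imbalanced, p<0.05 | 4.9% | 4.4% | 4.9% |
| Select if associated with outcome, p<0.05 | 5.0% | 5.3% | 5.3% |
| Select if both, p<0.10 | 4.9% | 4.4% | 4.5% |
| Select if either, p<0.05 | 5.0% | 5.2% | 5.3% |
| Better of unadjusted and the either-rule model | 5.2% | 6.8% | 7.7% |
| Best of unadjusted and six single-covariate models | 5.9% | 7.6% | 9.4% |
| Best of all 64 subsets | 6.7% | 9.5% | 12.6% |

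Repeat runs with other seeds and thresholds put the mechanical rules at 3.8-5.5% up to R² 0.30. The low end comes from selection on imbalance at R² 0.30.

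The better-of-two figure depends on the selection rule. With outcome-based, either-or or all-six selection it was 6.0-6.3% when each covariate correlates 0.1 with outcome (R² = 6 × 0.01 = 0.06), 7.4-7.6% at 0.2 (R² 0.24) and 8.5% at 0.3 (R² 0.54). If a covariate must be both imbalanced and prognostic, it was only about 5-6%.

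**4. Power.** For a single week-12 comparison with 99 per arm, 80% power needs 2.802 × √(2/99) = 0.398 SD. At a true difference of 0.40 SD and R² 0.30, adjustment for all six gives Φ(0.40/√(2 × 0.70/99) − 1.96) = Φ(1.40), about 92%. The simulation gives 91%, against about 81% when covariates enter only if imbalanced and about 80% unadjusted. At R² 0.12 the gap is about 83% against 80%.

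**The case against.** A reader might infer that the primary error rate is simply not 5%. The documents do not support that. A data-driven rule followed mechanically stays close to 5% or slightly below it. Inflation needs someone to look at several results and keep the favourable one, and no section plans that.

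A reader might also infer that the primary p-value depends on covariate choice in every case. Section 9.2 powers a group-by-time effect, and section 9.5.1 defines the outcome as "continuous outcome of change in HAMD scores". For that contrast, with main-effect covariates, the objection is right: the choice is close to irrelevant. It does not close the matter. The Aim 1 text refers only to treatment effects at 12 weeks, section 9.2 allows follow-up of either interactions or main effects, and section 9.6 does not say how covariates would enter.

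Nor does the text prescribe significance tests at baseline; it speaks only of comparing and examining. The covariate-free model can fairly be read as the default, but the plan never says so.

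Blinding the statisticians limits a choice driven by direction. It does not hide the size of a two-sided p-value, which is the same whichever group is coded 1. That protection is partial.

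**Conclusion.** The point holds as a pre-specification defect in the primary analysis. The plan allows more than one primary result, and covariates may be picked from the trial's own data, so 5% control is not guaranteed for a week-12 group difference or for models with covariate-by-time terms. Chosen with results in view, the error rate would be about 6-9% for the better of two models under outcome-based selection, and up to about 13% over many sets. Applied mechanically it stays at about 3.8-5.5% up to R² 0.30. Selecting on imbalance could cost about ten points of power at R² 0.30, and much less if the covariates are weak.

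These sizes rest on six independent covariates of assumed strength and a single-time-point linear model. They show what the wording permits and do not predict what the trial team will do. No figure in the plan is wrong on this account. The point should be corrected before unblinding, but it does not undermine the design.

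**What to change.** Remove the sentence as a route to covariates and replace it with a fixed specification:
- **Covariates:** site and imaging (the stratification factors), plus a short list of variables measured before randomisation, for example age, sex and age of onset. They enter whatever the baseline table shows. In the Aim 2 models every participant is imaged, so only site applies.
- **Form:** state whether covariates enter as main effects only or also by time.
- **Contrast:** state whether the primary week-12 effect is the group difference at week 12 or the group difference in change from baseline.
- **Baseline table:** descriptive only, with no role in model choice.
- **Other adjustment:** label it as sensitivity analysis, including adjustment for instructor.

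Stating that the covariate-free model is primary would also restore a defined 5% test, but it gives up the precision from prognostic covariates.

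The cost is SAP wording and a few degrees of freedom. With a fixed set the simulated error rate is 4.9-5.5%, nominal within Monte Carlo error, and d = 0.32 and the sample size stand.

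### The primary HAMD-24 model estimates a separate baseline mean in each arm, which costs precision at week 12, and the stated 0.32 SD holds only for a linear time coding that the analysis section does not fix

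*Combined protocol and SAP*

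**What the plan says.** Section 9.5.1 defines the primary outcome as the "continuous outcome of change in HAMD scores". Section 9.6 (Aim 1) models it with a "GLMM for HAMD-24 with treatment group effects and time main effects, along with two-way interactions of time and group" and adds: "The primary analysis will assess treatment effects at the end of treatment at 12 weeks". The same section says: "To make the most efficient use of our data we will fit a single model using all time points for each outcome". It plans to plot the trajectories first to look at their form. The only covariates it mentions are demographic and illness-course variables, to be used if needed.

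Section 9.2 counts baseline among seven time points (weeks 0, 2, 4, 6, 8, 10 and 12). It sizes the trial for a "treatment and time interaction corresponding to no difference at baseline" and 0.32 SD at the end of treatment, with 99 complete subjects per arm, alpha 0.05, 80% power and a correlation of 0.5 between time points. The figure is conditional: "if the treatment main effects are linear over the 12 week treatment phase on HAMD". If an effect is significant, follow-up contrasts are to show "at which time points there has been significant change and/or differences in treatment effects relative to baseline".

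Section 6.2.2 randomises subjects after screening and baseline results have been reviewed. Section 9.3 limits the ITT set to randomised subjects with a baseline assessment. Appendix A shows HAMD at both Baseline 1 and Baseline 2, and section 6.2.4 makes the second conditional on the gap between the visits.

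**The concern.** Baseline is treated as a response and the model contains a group effect, so the difference between arms at baseline is a free parameter. Under randomisation its expected value is zero, and section 9.2 sets it to zero when computing power. Estimating it adds noise to the change in HAMD, which is the primary outcome. Nothing in the plan constrains it or names baseline HAMD-24 as a covariate.

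The size of the loss, and the detectable effect itself, depend on how time is coded. Section 9.2 assumes a straight line for power; section 9.6 says neither linear nor categorical. A reader therefore cannot tell which detectable effect belongs to the week-12 test.

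**Working it through.** **Inputs.** From section 9.2: n = 99 per arm, seven visits, correlation ρ = 0.5 between any two visits, alpha 0.05, power 80%. Assumed: two-sided test (sidedness is not stated; two-sided reproduces 0.32, one-sided gives 0.283), SD of 1 at every visit, complete data, no clustering by class. The multiplier is 1.960 + 0.842 = 2.802.

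**1. The plan's figure (linear time, free baselines).** Code the visits t = 0 to 6, so Σ(t − mean)² = 28. The variance of the arm difference in slope is 2(1 − ρ)/(28n) = 1/2772. Over six steps the SE is 6 × √(1/2772) = 0.1140, and 2.802 × 0.1140 = 0.319. This matches 0.32.

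**2. Linear time, common baseline.** The information per arm is t′V⁻¹t = [Σt² − ρ(Σt)²/(1 + 6ρ)]/(1 − ρ) = 2 × (91 − 0.125 × 441) = 71.75, against 28/(1 − ρ) = 56 with free baselines. The variance ratio is 56/71.75 = 0.780, and the detectable effect is 0.319 × √0.780 = 0.282.

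**3. Categorical visits, free baselines.** The change contrast has variance 2 × 2(1 − ρ)/n = 2/99. The SE is 0.1421 and the detectable effect 0.398.

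**4. Categorical visits, common baseline.** The variance is 2(1 − ρ²)/n = 1.5/99. The SE is 0.1231 and the detectable effect 0.345. The variance ratio is (1 + ρ)/2 = 0.75, equivalent to 99/0.75 = 132 completers per arm under free baselines.

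| Time coding | Baseline | Detectable effect (SD) | Power at 0.32 SD |
|---|---|---|---|
| Linear, 12 weeks | free | 0.319 | 80% |
| Linear, 12 weeks | common | 0.282 | 89% |
| Categorical | free | 0.398 | 61% |
| Categorical | common | 0.345 | 74% |

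**5. Sensitivity to the correlation (assumed values).** For ρ = 0.3 and 0.7 the categorical saving 1 − (1 + ρ)/2 is 35% and 15%. The linear saving is 36% and 11.5%.

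**6. Sensitivity to unequal SDs (assumed values).** Let the baseline SD be k times the follow-up SD. The categorical saving is (k − ρ)²/(k² + 1 − 2ρk). At ρ = 0.5:
- k = 0.9: 0.16/0.91 = 18%
- k = 0.8: 0.09/0.84 = 11%
- k = 0.7: 0.04/0.79 = 5%

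A smaller baseline SD is plausible, because section 4.1 requires HAMD above 14 at baseline and nothing truncates later scores.

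**7. Shape check for the linear version.** Take a true week-12 difference of 1.
- Rises to week 6, then flat: the differences by visit sum to 5 and Σtd = 19.667. Free-baseline line: 6 × (19.667 − 15)/28 = 1.00. Constrained line: 6 × 2 × (19.667 − 13.125)/71.75 = 1.09.
- Zero to week 6, then linear: the differences sum to 2 and Σtd = 10.667. Free: 6 × (10.667 − 6)/28 = 1.00. Constrained: 6 × 2 × (10.667 − 5.25)/71.75 = 0.91.

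For these two shapes the distortion comes from adding the constraint to the straight line. With categorical visits the constraint leaves the week-12 contrast unbiased whatever the shape.

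**The case against.** The planned model is standard and valid, and 0.32 SD is right under its own condition. The pilot suggests a much larger effect: "Our R21 project found an effect size of 0.65 in HAMD between TCC and HEW at 12 weeks". At 0.65 SD, power exceeds 99% in all four versions. The plan names week 12, ties its hypotheses to contrasts and keeps the statisticians blind to group, which limits the scope for choosing a form of time to suit the result. All of this stands, and it makes the point an efficiency recommendation rather than a correction of an error.

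The saving also rests on assumptions. Section 9.2 leaves the covariance structure to be selected from the data, and gives no SDs. With an assumed random-slope variance of 0.1 to 0.3, the saving is 23% to 19% (categorical) or 19% to 15% (linear). This too stands, so 25% should not be quoted without its conditions.

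It might be said that the target is the week-12 level rather than the change. At ρ = 0.5 with equal SDs and categorical visits, the two have the same free-baseline variance (2/n), so the 25% holds for either.

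The baseline ambiguity is narrow: sections 6 and 6.2.2 treat visit 4 as the baseline mood assessment, and only the conditional repeat leaves doubt.

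Three stronger readings are tempting, and the documents do not support them:
- **That 0.32 SD is a mistake.** It reproduces at 0.319.
- **That the trial has only 61% power.** That follows only if visits are categorical with free baselines, and section 9.6 does not commit to categorical visits. The time-point contrasts in section 9.2 come after a significant result and do not settle the primary coding.
- **That a common baseline is free under any coding.** With a straight line it trades precision against shape. Nor is the free-baseline line always the safer one: for a plateau from week 4 it gives 86% of the week-12 truth against 101% for the constrained line, and for a start after week 8, 86% against 76%.

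**Conclusion.** The point holds as a loss of precision. With categorical visits, dropping the separate baseline means is an unbiased gain: 25% less variance, and 0.398 to 0.345 SD, at n = 99, ρ = 0.5 and equal SDs. Over the assumed ranges the saving runs from 35% to 15% for ρ of 0.3 to 0.7, and is about 18%, 11% or 5% for a baseline SD of 0.9, 0.8 or 0.7 of the follow-up SD. With a 12-week linear term the saving is 22%, but it carries the shape trade-off.

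The unfixed time coding matters at least as much. Under the same free-baseline model, the detectable effect is 0.319 SD if time is linear and 0.398 SD if it is categorical. The gain is of practical use if the true effect is nearer 0.32 than 0.65. None of these figures allows for clustering by class.

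**What to change.** In section 9.6, Aim 1:
- State that the arms share a common baseline mean, or use baseline HAMD-24 as a covariate. Define baseline as the last score before randomisation.
- State the coding of time before data are seen. Categorical visits with a common baseline is the version whose week-12 contrast needs no assumption about shape.
- Name the week-12 arm difference as the single primary contrast.

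In section 9.2, restate the detectable effect for the chosen model. For categorical visits with a common baseline it is 0.345 SD (n = 99, ρ = 0.5, equal SDs, before class clustering). Do not replace 0.32 with the more optimistic 0.282 unless the linear-shape, equal-SD and no-clustering assumptions are stated beside it. With classes of 6 or 7 (section 6.2.2), an assumed intraclass correlation of 0.01 to 0.05 and design effect 1 + (m − 1) × ICC (1.05 to 1.30), 0.345 becomes 0.353 to 0.393 and 0.282 becomes 0.289 to 0.322.

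Cost: no new data or visits, and no subjects lost, since the ITT set already requires a baseline assessment. The price of categorical visits is candour about power: 0.32 becomes 0.345 SD, and power at 0.32 SD is 74% rather than the stated 80%. Power at the pilot effect of 0.65 stays above 99%.

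### The week-12 remission model and the Hypothesis 2c mediation regressions pre-specify no baseline covariate; the tests stay valid but give up power, about 5–7 points for remission at the plan's correlation of 0.5 and d = 0.32–0.50

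*Combined protocol and SAP*

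**What the plan says.** On remission at week 12, section 9.6 (Aim 1, secondary analysis) states: "Secondary analysis will also include comparison of remission status (binary outcome) at the end of treatment between treatment groups via a logistic regression". Neither a covariate nor an effect measure is named.

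Under Exploratory Hypothesis 2c in the same section, the plan states that "we will assess the treatment mediator effects of change in DMN connectivity on change in HAMD and memory and executive function domain scores". The equations are given as follows: "the posited mediator variable is regressed on treatment, outcome is regressed on treatment and the outcome is regressed on the mediator and the treatment". None of the three has a baseline term.

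The general covariate text in 9.6 lists demographic variables and features of the depressive illness as examples, to be compared between groups and related to outcome. It concludes that "this would define one possible set of appropriate covariates, if needed". Baseline HAMD-24 and baseline DMN connectivity are not among the examples.

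The baseline data will exist. Appendix A schedules the HAMD at both screening and baseline, and MRI at screening/baseline for the scanned subset.

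**The concern.** For the outcomes analysed by GLMM, all time points go into one model, so the baseline measurement contributes. The remission and mediation analyses are separate regressions, and baseline acts as a covariate there only if the plan puts it in.

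Two things are at stake. The first is precision. Baseline severity should predict week-12 severity, and so remission, and the plan itself assumes a correlation of 0.5 between visits. The second is chance imbalance. Section 6.2.2 stratifies on site and imaging only, so nothing balances severity by design. One standard error of baseline imbalance with 99 per arm is √(2/99) = 0.14 SD. At correlation 0.5 that moves the week-12 contrast by 0.07 SD, about a fifth of the design effect of 0.32.

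Because covariates are left open until the data have been examined, the choice of whether to adjust is also not fixed in advance.

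**Working it through.** **Inputs from the documents.** Section 9.2 states that the design "with complete data on 99 subjects within each arm (10% dropout) will have 80% power", at α = 0.05, "for detecting a treatment and time interaction corresponding to no difference at baseline" and d = 0.32 SD at week 12, over 7 visits. It adds that "the reported power analysis is based on a correlation of 0.5 between measurements obtained at different time points". The pilot effect is 0.65. For imaging, 9.2 uses 55 complete subjects per arm and d = 0.53.

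**Assumptions.** Tests are two-sided (sidedness is not stated). The HEW remission rate is 20–35%. The documents give neither a HAMD cut-off for remission nor an expected HEW rate; the only anchor is the 30–35% cited in section 2.2 for antidepressant trials in older adults.

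**Reproducing the plan's figure.** Scale time 0 to 1 over 7 equally spaced visits, with compound symmetry:
- Σ(t − t̄)² = 0.7778, so the slope variance per subject is (1 − 0.5)/0.7778 = 0.643.
- SE of the group difference = √(2 × 0.643/99) = 0.114.
- Power = Φ(0.32/0.114 − 1.96) = 80.2%, against the stated 80%.

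The inputs are therefore read as the plan meant them.

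**Remission.** Baseline and week-12 scores were simulated as bivariate normal with correlation 0.5 and a TCC shift of d. Remission is a week-12 score below the cut-off that gives the assumed HEW rate. Each of 20,000 trials per cell, with 99 per arm, was analysed by a logistic Wald test without and with baseline. Entries are power in %, without → with; gains are taken before rounding.

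| d | HEW 20% | HEW 30% | HEW 35% |
|---|---|---|---|
| 0.32 | 36.6 → 42.1 (+5.5) | 40.5 → 46.8 (+6.2) | 43.0 → 48.6 (+5.6) |
| 0.40 | 53.9 → 60.7 (+6.8) | 58.9 → 66.2 (+7.4) | 61.3 → 67.8 (+6.6) |
| 0.50 | 74.0 → 80.5 (+6.5) | 78.8 → 84.5 (+5.7) | 80.3 → 85.8 (+5.6) |
| 0.65 | 93.1 → 96.1 (+3.0) | 95.0 → 97.3 (+2.3) | 95.7 → 97.6 (+2.0) |

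Checks:
- A two-proportion formula gives 41.4% for the unadjusted cell at d = 0.32 and HEW 30%, close to the simulated 40.5%.
- With d = 0, rejection in favour of TCC was 2.2% without and 2.3% with baseline, against a nominal 2.5%. Both tests hold their level.

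Sensitivity to the correlation, at HEW 30% with 6,000 trials per cell:
- At 0.3, power goes from 41.4% to 43.6% at d = 0.32 and from 58.4% to 61.2% at d = 0.40. Over other cells the gain is about 0–4 points.
- At 0.7 the gain is about 16 points.

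**Mediation, one treatment path.** In units of the cross-sectional SD, with correlation ρ = 0.5:
- The SD of a change score is √(2(1 − ρ)) = 1.00. Subtracting baseline therefore gains nothing over using the week-12 value alone.
- The residual SD after baseline adjustment is √(1 − ρ²) = 0.866.
- Change score: SE = √(2/55) = 0.191; power = Φ(0.53/0.191 − 1.96) ≈ 79%.
- Baseline-adjusted: SE = 0.866 × 0.191 = 0.165; power = Φ(0.53/0.165 − 1.96) ≈ 89%.

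Section 9.2 gives the 0.5 in its HAMD calculation; using it for DMN connectivity is an assumption.

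**The case against.** **The plan is silent; it does not exclude baseline.** This stands. Naming a logistic regression does not make treatment the only term, and the covariate text is open-ended. A reader might infer that baseline has been ruled out, and the documents do not say so. What is missing is pre-specification.

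**Change scores already use baseline.** This also stands. It would be wrong to say that the mediation models ignore the baseline value, because it enters by subtraction. At correlation 0.5, however, subtraction brings no reduction in variance, while a covariate does.

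**There is no bias to correct.** Correct. Under 1:1 randomisation the unadjusted comparison is valid, and the simulation shows its error rate held. The gain is efficiency only, in a secondary and an exploratory analysis for which the plan claims no power.

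**The size depends on favourable inputs.** Partly right. The only TCC-versus-HEW effect on HAMD that the documents report is 0.65, where the gain is 2–3 points. Baseline to week 12 is the longest gap in the treatment phase, so its correlation may be below a common 0.5. Entry also requires HAMD above 14. If 0.5 describes an unrestricted population, truncating baseline at −1, −0.5 or 0 SD lowers the correlation to about 0.42, 0.37 or 0.33. The gain at d = 0.32–0.40 then falls to 4–5, about 3 and about 3 points. The documents do not say which population the 0.5 describes.

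**A joint power figure for mediation.** Mediation is confirmed only if treatment is significant on both mediator and outcome, so it is tempting to multiply two path powers. The documents do not support this. The product treats the tests as independent, which mediation itself contradicts, and it applies an imaging effect size to the HAMD path. Moreover, the outcome-on-treatment equation needs no scan and is not stated to be confined to the imaging subset.

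**Conclusion.** The point holds as a free gain in efficiency. No baseline covariate is pre-specified for the remission model or the three mediation equations, although the data are collected.

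For remission, the gain from adjustment is about 5–7 power points at d = 0.32–0.50, 2–3 points at d = 0.65, and about 0–4 points if the correlation is 0.3. These figures rest on 99 per arm, an assumed HEW rate of 20–35%, the plan's correlation of 0.5 (except in the last figure), and a simulation that ignores clustering by class and the HAMD entry cut-off. For one mediation path, power is about 79% against 89%, conditional on the 0.5 carrying over to DMN connectivity.

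A reader might go further and conclude that the remission result would be biased, or that the trial's main conclusion is weakened. Neither follows: the unadjusted tests are valid, and the primary HAMD-24 GLMM and the Aim 2 co-primary GLMMs already include baseline as a repeated measure.

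**What to change.** In section 9.6:

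- **Remission.** State that the logistic model will include continuous baseline HAMD-24 as a pre-specified covariate. Report the standardised (marginal) risk difference with its interval beside the adjusted odds ratio.
- **Mediation (Hypothesis 2c).** Add the baseline value of the outcome concerned (HAMD or the cognitive domain score) and baseline DMN connectivity to all three equations. The change scores can stay: once baseline is a covariate, the treatment coefficient is the same whether the response is change or the week-12 value.
- **Definition of baseline.** Because the HAMD may be taken at both screening and baseline, say which pre-randomisation score is used.

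The cost is a sentence or two in each place, with no new data or visits. The one drawback is that the adjusted odds ratio is conditional on baseline and differs from the crude one; the standardised risk difference deals with that.
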